Vortioxetine improved cognition sub-items in the Montgomery-Åsberg Depression Rating Scale (MADRS) [44] (Item 6 — concentration difficulties) [45] and Hamilton Anxiety Scale (HAM-A) [46] (Item 5 - concentration and memory) [47] when compared to placebo (in the trials in which the primary endpoint was also positive). In addition, exploratory cognitive tests for verbal learning (RAVLT — Rey Auditory Verbal Learning Test) [48] and executive function, working memory, processing speed and visuospatial attention DSST [49]) were included in a vortioxetine conducted study in elderly patients [50] with MDD (primary endpoint was change in depressive symptoms). In this study, vortioxetine 5 mg/day improved cognitive dysfunction in both tests whereas duloxetine (active reference) improved cognitive dysfunction in the RAVLT but not in the DSST. This finding is consistent with the literature as shown by a study in which elderly patients receiving duloxetine demonstrated significantly greater improvement in a composite cognitive score mainly driven by improved verbal learning and memory [51].

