    - i. Subjects meeting antidepressant efficacy criteria (based on response and remission criteria for MADRS, HRSD, QIDS) and improvement in cognition (based DSST).
    - ii. Subjects failing to meet antidepressant efficacy criteria (based on response criteria for MADRS, HRSD, QIDS) but show improvement in cognition (based on DSST).
    - iii. Subjects failing to meet antidepressant efficacy criteria (based on response criteria for MADRS, HRSD, QIDS) and failing to show improvement in cognition (based on DSST).
    - iv.
    - v.
- 5. To explore changes in BNA patterns in MDD with cognitive dysfunction prior to receiving treatment with vortioxetine and:
  - a. Severity of MDD as measured by baseline MADRS total score, QIDS-SR-16 total score, HDRS-28 item total score and CGI-Severity.
  - b. Severity of cognition dysfunction and functionality as measured by baseline DSST, TMT-A/B, TMT-B, Stroop, MGH-CPFQ total score, UPSA, WLQ.
  - c. Prediction of achieving symptomatic remission of MDD as measured by remission status on MADRS total score, HDRS-17 total score and CGI-Improvement (1 or 2)
  - d. Prediction of cognitive improvement measured by DSST score; cutoff 70% improvement from baseline.
- 6. Explore relationship with changes in BNA patterns in remitted vs. non-remitted subjects after 8 weeks of treatment with vortioxetine as measured by MADRS total score, HDRS-17 total score, QIDS total score,, and CGI-Improvement.
- 7. Assess safety and tolerability of 8 weeks open-label, flexible-dose vortioxetine in all subjects for:
  - a. Spontaneously reported adverse events
  - b. Clinical safety laboratory tests (when indicated, vital signs, weight, EKGs and physical exam)

- c. Evaluate relationship between adverse events after 2 and 8 weeks of treatment with changes in BNA patterns for nausea, worsening of baseline suicidal ideation (as measured by MADRS item 10, HDRS-17 item 2 and C-SSRS)

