#### **DESCRIPTION OF CLINICAL OUTCOME MEASURES**

##### ***DEPRESSION:***

##### **Montgomery and Åsberg Depression Scale (MADRS)**

The MADRS is a 10-item rating scale designed to assess the severity of the symptoms in depressive illness that was shown to be sensitive to treatment effects. Items in the scale assess apparent sadness, reported sadness, inner tension, reduced sleep, reduced appetite, concentration difficulties, lassitude, inability to feel, pessimistic thoughts and suicidal thoughts. Symptoms are rated on a 7-point scale from 0 (no symptom) to 6 (severe symptom). Definitions of severity are provided at 2-point intervals. The total score of the 10 items ranges from 0 to 60. An experienced clinician can use the MADRS after a training session. It takes approximately 15 to 20 minutes to administer and rate the MADRS. All efforts will be made to keep the rater consistent.

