##### **Hamilton Depression Rating Scale (HDRS)**

The HDRS is a clinician-rated used to rate the patient's depressive state based on feelings of depression, guilt, suicidality, anxiety, agitation, level of insight, patterns of insomnia, loss of interest in work and other activities, weight loss, hypochondriasis, and degree of psychomotor retardation. It also can be used to identify genital and somatic symptoms. This instrument will be administered by an experienced rater meeting the training requirements and qualifications set by the rater training vendor. All efforts will be made to keep the rater consistent.

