### **Secondary Efficacy Analyses**

Change from Baseline in TMT A, TMT B, , PDQ, MGH-CPFQ, UPSA, percentage of productivity loss (WLQ), MADRS, CGI-S, and CGI-I will be analyzed at all time points (where rated) using ANCOVA model similar to the one described above for the primary endpoints.

MADRS responders (defined as a >50% decrease from Baseline), MADRS remission (defined as a MADRS total score <10). CGI-S remission (CGT-S2), and CGI-I response (CGI-I2) will be analyzed at all time points by logistic regression, adjusting for baseline score and treatment.

Proportion of cognitive dysfunction improvement that is not due to an improvement in depressive symptoms will be analyzed using a path analysis with change from Baseline in DSST score and change from Baseline in MADRS total score as endogenous variables.

C-SSRS will be summarized at all time points using descriptive techniques.

All statistical tests will be 2-sided and at the 5% level of significance. Ninety-five percent confidence limits will be presented together with the p-values.

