### **Outcome Definitions**

- Remission (Primary Remission Criteria)
  - MADRS total score  $\leq$  10; CGI-I  $<$  2
- Remission (Secondary Remission Criteria)
  - Score  $\leq$  7 of first 17 items of the HDRS (28-item)
  - QIDS-SR16 total score  $<$  5
- Asymptomatic Remission
  - MADRS total score  $\leq$  4
- Response (Primary Response Criteria)
  - $\geq$ 50% decrease in MADRS total score from baseline
- Response (Secondary Response Criteria)
  - $\geq$ 50% decrease from baseline of first 17 items of the HDRS (28-item)
  - $\geq$ 50% decrease from baseline in total score of HDRS (28-item)
  - $\geq$ 50% decrease from baseline in total score of QIDS-SR 16
  - $\geq$ 50% decrease from baseline in total score of MGH-CPFQ
- Non-Remitted (Primary)
  - MADRS total score  $>$  10
- Non-response
  - Change in MADRS total score from baseline  $<$  25%, and MADRS total score  $>$  10
- Inadequate response
  - Change in MADRS total score from baseline 25-49%, and MADRS total score  $>$  10

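### Outcome 7c cites HDRS-17 item 2 for suicidal ideation, but the protocol's own HDRS description names guilt second and suicidality third; the item number needs checking

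*Combined protocol and SAP*

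**What the plan says.** Item 7 of the Secondary Outcomes covers safety and tolerability. Part 7c relates BNA changes to adverse events after 2 and 8 weeks, and the events include "worsening of baseline suicidal ideation (as measured by MADRS item 10, HDRS-17 item 2 and C-SSRS"). Three measures are named, two of them by item number.

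The paragraph on the HDRS, under Description of Clinical Outcome Measures, is the only account of that scale's content. It says that the rating rests on "feelings of depression, guilt, suicidality, anxiety, agitation, level of insight, patterns of insomnia, loss of interest in work and other activities", then names weight loss, hypochondriasis and psychomotor retardation. A separate sentence follows: "It also can be used to identify genital and somatic symptoms". No items are numbered there or elsewhere in the document. Outcome Definitions scores the 17-item version as a total "of first 17 items of the HDRS (28-item" version), and the Schedule of Events lists the 28-item form at all ten visits.

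The MADRS paragraph names ten items for a ten-item scale, ending "lassitude, inability to feel, pessimistic thoughts and suicidal thoughts". The Introduction cites another MADRS item by number: "Item 6 — concentration difficulties".

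On analysis, Secondary Efficacy Analyses says "C-SSRS will be summarized at all time points using descriptive techniques". Neither the efficacy nor the safety statistics describe an analysis of a single HDRS item.

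**The concern.** An analyst programming outcome 7c would take the item number literally and pull item 2 from the HDRS data. If that item rates guilt, the HDRS part of the outcome measures something other than suicidal ideation. A subject whose guilt rises would register as worse on suicidality by this scale, and one whose suicidality rating rises while guilt stays level would not.

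The statistics section would not catch the slip, because it sets out no HDRS item-level analysis against which the number could be compared. With 40 subjects planned, and possibly few showing any worsening, one or two misclassified subjects could alter how an exploratory association with BNA change reads.

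**Working it through.** The plan gives no figure to reproduce. The check compares each cited item number with the place of that content in the protocol's own description of the scale.

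**1. MADRS, as a control.** The order in the MADRS paragraph is: (1) apparent sadness, (2) reported sadness, (3) inner tension, (4) sleep, (5) appetite, (6) concentration, (7) lassitude, (8) inability to feel, (9) pessimistic thoughts, (10) suicidal thoughts.

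| Citation | Content | Place in list | Agrees? |
|---|---|---|---|
| Introduction, item 6 | concentration | 6 of 10 | yes |
| Outcome 7c, item 10 | suicidal thoughts | 10 of 10 | yes |

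**2. HDRS.** The order in the HDRS paragraph is: (1) depression, (2) guilt, (3) suicidality, (4) anxiety, (5) agitation, (6) insight, (7) insomnia, (8) loss of interest, (9) weight loss, (10) hypochondriasis, (11) psychomotor retardation.

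| Citation | Content | Place in list | Agrees? |
|---|---|---|---|
| Outcome 7c, item 2 | suicidal ideation | 3 of 11 | no; place 2 is guilt |

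**3. Does the shortness of the HDRS list rescue item 2?** The list has 11 entries for a scale of 17 or 28 items, so it cannot match the items one to one. Suppose that it keeps the order of the form but merges some items into one entry and leaves others out. At least *k* − 1 items then come before the entry in place *k*, so its item number is at least *k*. For suicidality *k* = 3, which gives item 3 or later. Merging and omission can only push the number up. Item 2 could be suicidality only if the list departs from form order within its first three entries, or if depression and guilt share a single item. Nothing in the documents suggests either, but unnumbered prose cannot exclude them.

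**4. Does the 17-item or 28-item version matter?** No. The 17-item score is taken from the first 17 items of the 28-item form, so item 2 is the same item in both, and one form settles the question.

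**5. Consequence if item 2 is guilt.** It depends on how the three measures are combined, which the plan does not say.

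| Rule (assumed) | Effect |
|---|---|
| Any one of three suffices | A rise in guilt alone counts as worsened ideation; a rise in HDRS suicidality counts only if the MADRS item or C-SSRS also shows it |
| All three required | True worsening is missed whenever guilt does not rise |
| Each reported separately | The HDRS result is mislabelled; the other two are correct |

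**The case against.** The strongest reply is that the HDRS paragraph is not an item list at all. It names areas of content in running prose, groups insomnia as patterns, and puts genital and somatic symptoms in a separate sentence. The MADRS paragraph, by contrast, says that it is listing items and gives exactly ten for a ten-item scale, so success of the position check there does not show that the HDRS summary follows form order. That stands. It makes the mismatch an inference, not a direct contradiction, and only the form can settle it.

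It is also fair that the consequence is limited. Outcome 7c is one exploratory relationship in a pilot study. The MADRS item number agrees with the protocol's own list, and the C-SSRS, a dedicated interview on suicidal ideation and behavior, is given at every visit. Under Other Risks, suicide risk at a visit is judged by the examining clinician, not by an HDRS item number. Because the whole HDRS is collected, a wrong citation could be put right at analysis with no data lost.

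What the reply does not supply is any support for item 2. The protocol's only description points away from it, and the shortness of the list does not help, as step 3 shows.

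A reader might go further and infer that the safety analysis will use the wrong item, or that every HDRS-based suicidality classification is wrong. The documents do not support that. They contain no HDRS form, define no such classification, give no threshold or combination rule, and name two other measures that are not in doubt.

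**Conclusion.** The item number in outcome 7c does not fit the protocol's own description of the HDRS and may point to guilt. This is a strong indication, not proof. It rests on one assumption: that the HDRS paragraph follows the order of the form at least through its first three entries, with depression and guilt as separate items.

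The size is modest: one of three named measures, in one exploratory secondary outcome, for up to 40 subjects. The primary outcome, sample size, power and significance level are untouched. How many subjects would be misclassified cannot be computed, because the plan gives neither a combination rule nor expected rates of worsening. The point still deserves a correction and not just a note, because the number stands in an outcome definition that an analyst would follow to the letter.

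**What to change.** In Secondary Outcomes, item 7c, replace the reference to HDRS-17 item 2 with *the HDRS suicidality item*, and add its number once it has been verified against the 28-item form in use. Naming the content as well as the number is correct whichever number the form shows. It would help to state in the same place whether the three suicidality measures are reported separately or combined, and by what rule.

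The cost is one phrase, one look at the form and, if wanted, one sentence on combination. The 28-item HDRS is already scheduled at every visit, so no assessment, visit or data field is added.

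The change should be made before the analysis is programmed.

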**Informed Consent:**

The informed consent document, in conjunction with verbal discussion of the protocol, will be used to explain the study, including the risks and benefits, to the subject in simple terms before the subject is entered into the study. The investigator is responsible to see that informed consent is obtained from each subject and to obtain the appropriate signatures and dates on the informed consent document prior to the performance of any protocol procedures and prior to any changes made to a subject's medical treatment plan for the purpose of study participation. The original signed consent form will be retained by the investigator.

All subjects will take part in the informed consent process prior to participating in any study specific assessments or procedures, including assessment of study specific inclusion and exclusion criteria. The principal investigator and his designee will conduct the informed consent process in compliance with Good Clinical Practice Guidelines. Subjects will then be eligible for Screening Visit.

**Subject Selection:**

Subjects will be screened for study inclusion and exclusion criteria, and the case report form (CRF) will be reviewed by the principal investigator prior to Baseline Visit (Visit 2).

**Main Criteria for Inclusion:**

- The subject has single episode or recurrent MDD (acute onset of recurrence of recurrent MDD with poor inter-episode recovery) (inter-episode periods cannot meet full MDD criteria) as the primary diagnosis according to DSM-IV-TR criteria. The current MDE will be confirmed using the Mini International Neuropsychiatric Interview (MINI V6.0.0).
- The subject has a MADRS total score  $\geq 26$ .
- Subject reports subjective cognitive dysfunction (such as difficulty concentrating, slow thinking, and difficulty in learning new things or remembering things).
- The reported duration of the current MDE is at least 3 months and no longer than 24 months.
- The subject is a man or woman between 18 and 65 years old, inclusive.
- Right-handed, normal (corrected) vision, and normal hearing.

**Main Criteria for Exclusion:**

- The subject has a score of  $\geq 70$  on the DSST at the Baseline Visit.
- Failure to respond to or inability to tolerate an adequate trial of vortioxetine in the past.
- Exposure to an investigational compound 30 days prior to enrollment
- Exposure to any psychoactive or otherwise excluded medication within five half-lives of the baseline visit or during the study. Excluded medications include: antidepressants, anxiolytics, anticonvulsants, barbiturates, chloral hydrate, lithium, antipsychotics, benzodiazepines, hypnotics, MAO-Inhibitors, muscle relaxers, triptans, centrally-acting antihistamines, central alpha-2 agonists, decongestants, psychostimulants, dopamine agonists, opioid pain medications, oral corticosteroids, L-methylfolate, SAMe, 5-HTP, St. John's Wort.
- The subject has 1 or more of the following:
  - Primary psychiatric disorder other than MDD as defined in the DSM-IV-TR (as assessed by the MINI, Version 6.0.0).

- Current or history of attention deficit hyperactivity disorder (ADHD), pervasive developmental disorder, manic or hypomanic episode, schizophrenia, or any other psychotic disorder, including major depression with psychotic features, mental retardation, organic mental disorders, or mental disorders due to a general medical condition as defined in the DSM-IV-TR.
- Current diagnosis of alcohol or other substance abuse or dependence (excluding nicotine or caffeine) as defined in the DSM-TV-TR that has not been in sustained full remission for at least 6 months (for abuse) and 12 months (for dependence) prior to Screening.
- Positive urine drug screen prior to Baseline.
- Presence or history of a clinically significant neurological disorder (including epilepsy) or severe head injury, or any condition that has caused an abnormal EEG or that may interfere with an EEG recording in the opinion of the investigator.
- Neurodegenerative disorder (Alzheimer Disease, Parkinson Disease, multiple sclerosis, Huntington Disease, etc).
- Any unstable medical condition as determined by the principal investigator (PI).
- Any DSM-IV Axis II disorder that might compromise the study as determined by the PI.
- The subject has any other disorder for which the treatment takes priority over treatment of MDD or is likely to interfere with study treatment or impair treatment compliance.
- The subject has physical, cognitive, or language impairment of such severity as to adversely affect the validity of the data derived from the neuropsychological tests.
- The subject has a significant risk of suicide according to the PI's clinical judgment.
- The subject, in the opinion of the PI, poses a risk of harm to others.
- The subject has initiated formal cognitive or behavioral therapy, systemic psychotherapy within less than 6 months of study screening, or has plans to initiate such therapy during the study.
- The subject has received electroconvulsive therapy, vagus nerve stimulation, or repetitive transcranial magnetic stimulation within 12 months prior to Screening.
- The current MDE is considered by the PI to have been resistant to 2 adequate antidepressant treatments of at least 6 weeks duration each at the recommended dose.
- The subject is pregnant or breastfeeding, or is intending to become pregnant before, during, or within 30 days after participating in this study.
- Hair or scalp conditions that may significantly compromise the quality of an EEG with 64 scalp electrodes, including but not limited to braids or significant alopecia, in the opinion of the investigator (collaboration with EIMindA will be sought if unclear).

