### Study Synopsis

This study will include adult outpatients 18-65 years of age with major depressive disorder (MDD) with subjective reporting of cognitive dysfunction treated with flexible-dose vortioxetine (5-20 mg/day) for eight weeks. Following completion of the informed consent process, this study will consist of a screening period (visit 1) of 2-14 days to assess inclusion/exclusion criteria. Subjects who continue to meet inclusion criteria at baseline (visit 2) will begin the assessment and treatment phase of the study.

The first EEG/BNA (BNA) will be performed at the screen visit. Subsequent BNA will be at baseline, 2-weeks after the start of treatment, and at the end of 8 weeks of treatment (or early termination).

The Schedule of Events (Appendix I) shows detailed study procedures that will be performed at each visit. The table below clarifies the schedule of dosing and attendant BNA tests.

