### **STUDY PROCEDURES**

See Schedule of Events (Appendix I) for complete list of study procedures performed at each visit.

All BNA procedures will be done as early in the visit as possible to avoid any confounding factors that may impact the outcome, except during the screen visit (at this visit, the BNA will occur after the subject completes the informed consent process and clinician-assessed inclusion/exclusion criteria are assessed). The screening visit can be split into 2 visits, as long as the screening period does not exceed the 14-day screen period.

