### **Visits 2-10**

#### All Subjects

- Subjects who meet all inclusion criteria and no exclusion criteria following the screening visit will enter the study. Weekly study visits will be conducted for efficacy, safety, and tolerability. No dose changes will be allowed after Visit 8.
- A baseline EEG/BNA will be taken before the subject begins taking vortioxetine and follow-up EEG/BNA readings will be taken at Visit 4, and Visit 10 (or last study visit if a subject is withdrawn early).
- Vital signs, review of adverse events, study drug accountability and clinician- and patient-rated scales will be conducted at specific study visits.

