## **STATISTICAL ANALYSES**

### **Primary Efficacy Analysis**

The primary endpoint is the change from Baseline in the MADRS and DSST score. The primary endpoint will be analyzed using analysis of covariance (ANCOVA), with treatment and center as fixed factors, and baseline score as covariate. The p-values, least squares (LS) treatment means, difference between the LS treatment means, and 95% CIs for the treatment differences will be displayed.

This is a pilot study that is intended to evaluate the extent of to which BNA technology can provide clinically valuable information, and to provide data that will help design a future confirmatory study. Because this is an exploratory study, no formal sample size calculation was performed; rather, sample size has been based on that which is generally accepted by the medical community for a study of this nature. In order to strengthen the level of confidence of the results, the BNA test is performed twice before the subject is given medication to provide repeatability and two additional times during the course of treatment to allow the identification of any potential trend that may occur as a result of treatment.

The relationship between changes in BNA and BNA total mean change from baseline and endpoint will be analyzed. Changes in BNA from baseline will also be analyzed by groups defined on endpoint status (e.g. response to MADRS, remission, change in DSST).

Statistical analysis should also consider the fact that changes in brain networks may be independent of symptoms or neurocognitive scores; thus, the analysis of BNA changes across treatment duration should be also performed independently. In other words, it is possible that BNA conveys information that is not found in other methods; trying to find correlations may limit the correct interpretation. Therefore, robust trends found in BNA scores should be further researched, regardless of finding correlations to symptoms or neurocognitive tests. For example, it could be that a change in BNA, without a significant change in symptoms, means that if the treatment will be continued for a few more weeks, a delayed improvement will be found; etc.

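### The drug-free rule counts back from Baseline, but the first BNA and the only scheduled pre-treatment DSST, UPSA, TMT and Stroop are at Screen, so drug removal can enter BNA repeatability and cognitive change.

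*Combined protocol and SAP*

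**What the plan says.** **The rule.** Main Criteria for Exclusion bars "Exposure to any psychoactive or otherwise excluded medication within five half-lives of the baseline visit or during the study". The list that follows includes antidepressants, benzodiazepines, hypnotics and psychostimulants. Nearby criteria on substance use, device-based treatment and psychotherapy are counted from Screening. This one is counted from Baseline.

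**The schedule.** Appendix I puts DSST, UPSA, TMT-A/B and Stroop at Screen and Visit 10 (or early termination) only. BNA is at Screen, Baseline, Visit 4 and Visit 10. Screen falls on Day -14 to Day -2.

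**The purpose of two pre-treatment BNAs.** Primary Efficacy Analysis says "the BNA test is performed twice before the subject is given medication to provide repeatability", and Secondary Objectives relies on the same pair to strengthen confidence in later patterns. For the Screen recording, Study Procedures says that "at this visit, the BNA will occur after the subject completes the informed consent process and clinician-assessed inclusion/exclusion criteria are assessed".

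**When the study begins.** The Synopsis says "this study will consist of a screening period (visit 1) of 2-14 days to assess inclusion/exclusion criteria", which makes screening part of the study. The Visits 2-10 section says "Subjects who meet all inclusion criteria and no exclusion criteria following the screening visit will enter the study", which puts entry after screening. Informed Consent requires signatures "prior to any changes made to a subject's medical treatment plan for the purpose of study participation".

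**Where the DSST is taken.** One exclusion criterion uses a score "on the DSST at the Baseline Visit", a test that Appendix I does not schedule.

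**The concern.** No section requires a subject to be drug-free when the Screen measures are taken. The criteria are assessed before the Screen BNA, but a subject can satisfy a rule anchored to Baseline by stopping a drug later. A urine drug screen is also listed, but its panel is not stated, so the documents do not show which excluded drugs it would detect.

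Two results are exposed. The first is BNA repeatability: the two pre-treatment recordings are meant to be repeats, yet they can differ in drug state. The second is cognitive change. If the reference score is taken under an earlier drug and the Week 8 score is not, the change includes removal of that drug. DSST change is the second part of the primary outcome and defines the cognition subgroups among the secondary outcomes. It also enters the path analysis beside MADRS change. MADRS is rated at Baseline and DSST, per Appendix I, is not, so drug removal could appear there as cognitive benefit independent of mood. The trial has no control arm against which to separate it.

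**Working it through.** The plan gives no figure to reproduce: no formal sample size calculation was done, and no washout share is stated. The check is therefore on timing, followed by an illustration of size.

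**1. Timing.** Inputs from the documents: five half-lives, and a Screen-to-Baseline gap G of 2 to 14 days. Assumed: half-life h from 0.5 to 7 days, and first-order elimination after the last dose. The share left at Baseline is at most 2^-5 = 1/32 = 3.1%.

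*Reading A: the study starts after screening.* Dosing on the Screen day meets the rule if 5h ≤ G, so h ≤ G/5:
- G = 2 days: 0.4 days = 9.6 h
- G = 7 days: 1.4 days = 33.6 h
- G = 14 days: 2.8 days = 67.2 h

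For longer half-lives the share left at Screen is 2^(-(5h-G)/h). With G = 14, h = 4 days gives 2^-1.5 = 35%, and h = 7 days gives 2^-3 = 12.5%.

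*Reading B: the study starts at consent.* Assume the last dose is one day before Screen, or earlier where the five-half-life rule demands it. Then L = max(5h, G+1) days before Baseline, and the share left at Screen is 2^(-(L-G)/h):

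| h (days) | G = 14 | G = 7 | G = 2 |
|---|---|---|---|
| 0.5 | 25% | 25% | 25% |
| 1 | 50% | 50% | 12.5% |
| 1.5 | 63% | 63% | 7.9% |
| 2.8 | 78% | 17.7% | 5.1% |
| 4 | 35% | 10.5% | 4.4% |
| 7 | 12.5% | 6.25% | 3.8% |

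On either reading, drug state at Screen can differ from drug state at Baseline. The difference is small when the gap is short and the half-life long.

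**2. BNA repeatability, illustration.** Assumed: unit SD at each recording, true repeat correlation 0.8, and a share p of subjects shifted by d SD in one direction. The SD of the Screen-Baseline difference is sqrt(2(1-0.8) + p(1-p)d²).
- No washout: sqrt(0.40) = 0.632
- p = 0.2, d = 0.5: sqrt(0.40 + 0.04) = 0.663, up 5%
- p = 0.5, d = 1: sqrt(0.40 + 0.25) = 0.806, up 27%

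The mean difference moves by p × d, from 0.2 × 0.5 = 0.1 SD to 0.5 × 1 = 0.5 SD.

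**3. DSST change, illustration.** If the earlier drug alters DSST by 2-5 points in 20-50% of subjects (8-20 of 40), mean change shifts by 0.2 × 2 = 0.4 to 0.5 × 5 = 2.5 points. For scale, take the SD of change as 1 and a shift of 0.5 SD in 25-50% of subjects. The mean then moves 0.125-0.25 SD, against a standard error of 1/sqrt(40) = 0.158 SD.

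**The case against.** The strongest reply is that the rule also forbids exposure during the study, and the Synopsis counts screening as part of the study. On that reading nobody is still taking an excluded drug at Screen. This stands as far as it goes: a reader might infer that subjects will be tested at Screen on full treatment, and the documents do not establish that. What remains on that reading is residual drug or withdrawal, and an unresolved conflict with the Visits 2-10 wording.

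No washout procedure is described, and the consent sentence is general wording. It is compatible with drugs being stopped after Screen but does not show that this happens. The number affected could be small.

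If the DSST is in fact done at Baseline, as the exclusion criterion implies, the DSST part largely falls away. UPSA, TMT, Stroop and the Screen BNA would still be exposed.

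A reader might also infer that improvement is necessarily overstated. That is not supported. The Introduction says some conventional antidepressants may worsen cognition, but it also reports that duloxetine improved verbal learning. Stopping a stimulant, or testing during withdrawal, could act the other way, and mixed drug classes could partly cancel.

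The Screen BNA also comes later in its visit than the other recordings. That is a disclosed exception, partly offset by the preference for the same time of day, and this point does not rest on it.

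**Conclusion.** The concern holds in limited form, with moderate confidence. As written, the plan permits the first BNA of the repeatability pair, and the only scheduled pre-treatment cognitive tests, to be taken before the five-half-life condition is met. The consequence is possible rather than certain and arises only in subjects who stop an excluded drug around screening.

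Every size above depends on the assumed share, effect and correlation. The DSST shift can go in either direction, and the BNA figures assume that all affected subjects shift the same way.

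It would go too far to say that the primary BNA result is contaminated. Objectives and Outcomes define that change from baseline to endpoint, and the Baseline recording comes after the five half-lives. The same protection covers MADRS change from Baseline. Nor do the documents make the Screen-Baseline difference a formal noise threshold: they use it to support repeatability and confidence, and an inflated difference would tend to make claims of BNA change more cautious.

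**What to change.** 1. Reconcile the Synopsis, Informed Consent, Main Criteria for Exclusion, Visits 2-10 and Appendix I on when the drug-free requirement starts relative to Screen, and on which visit supplies the reference DSST.
2. Schedule the pre-treatment DSST, UPSA, TMT and Stroop, and the first BNA where the window allows, at an attendance where the protocol's own five-half-life condition is already met. Study Procedures already allows screening to be split into two visits within 14 days. For the DSST, the Baseline Visit is an alternative that matches the existing exclusion wording.
3. Where that is not possible, flag the subject from the Visit 1 concomitant-therapy record, leave that Screen BNA out of the repeatability estimate, and report cognitive change with and without flagged subjects.

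This moves assessments and adds a sensitivity analysis; it changes no drug rule. The cost is a short amendment to Study Procedures and Appendix I, some second screening attendances, and slightly fewer Screen-Baseline BNA pairs. The split visit will not serve everyone. From Day -14 to a second attendance on Day -2 is 12 days, which covers five half-lives only up to 12/5 = 2.4 days (57.6 h) for a drug stopped on Day -14. The third step is therefore needed as well.
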